9.2. Documenting and Reporting of Adverse Events (Including Serious Adverse Events)

Adverse Events will be evaluated and documented using the grading scales contained in the National Cancer Institute Common Terminology Criteria for Adverse Events (NCI CTCAE) (Version 4.03).

9.2.1. Documenting and Reporting Adverse Events

All AEs reported from the time of informed consent to the end-of-study for each subject will be recorded in the subject's source documents. For subjects who do not receive study drug (ie, screen failures), AEs will only be recorded in the source documents. For subjects enrolled into the study (i.e., randomized), record all AEs in the subject's AE eCRF and Clinical Trials SAE Form (if applicable). The AE eCRF will indicate if the event occurred prior to the first dose of study drug, during treatment, or during the post-dosing follow-up period. Record all AEs regardless of the intensity, seriousness, or relationship to study drug.

Grade AEs (serious and non-serious) in accordance with the NCI/CTCAE scale (available at https://evs.nci.nih.gov/ftp1/CTCAE/CTCAE_4.03_2010-06-14_QuickReference_8.5x11.pdf) as presented below:

- **Mild** (Grade 1) asymptomatic or mild symptoms; clinical or diagnostic observations only; intervention not indicated
- **Moderate** (Grade 2) minimal, local or noninvasive intervention indicated; limiting age-appropriate instrumental activities of daily living
- **Severe** (Grade 3) Severe or medically significant but not immediately life-threatening; hospitalization or prolongation of hospitalization indicated; disabling; limiting self-care activities of daily living

- **Life-threatening** (Grade 4) Life-threatening consequences; urgent intervention indicated
- **Death** (Grade 5) Death related to the AE.

Any recurrence of an AE with similar causality to study drug will be reported as recurrence or exacerbation of the initial event, and not as a new event. Whenever possible, report AEs as a specific diagnosis or syndrome (eg, flu syndrome) rather than as individual signs or symptoms. If no specific diagnosis or syndrome is identified, AEs should be reported as separate and individual events.

An AE includes the following:

- Progression or exacerbation of the subject's underlying disease. Clinical sequelae that result from disease progression, such as pleural effusion or small bowel obstruction, are reportable as AEs.
- Pre-existing event that increases in frequency or intensity
- Condition detected or diagnosed during the study period, even though it may have been present, in retrospect, prior to the first dose of study drug
- Laboratory abnormalities outside of normal limits and requiring therapeutic intervention
- An overdose of the study drug without any signs or symptoms – a calculated dose that exceeds its correct dose by 10% or more and is administered to the subject will be considered an overdose and documented as an AE.

The following events **will not** be identified as AEs in this study:

- Medical or surgical procedures (eg, surgery, endoscopy, tooth extraction, etc); however, the condition (the “triggering event”) that leads to the procedure may be an AE.
- Pre-existing conditions present or detected prior to the first dose of study drug that do not worsen.

9.2.2. Assigning Attribution of Adverse Events

The Investigator must attempt to determine the cause of each event. Every effort will be made by the Investigator to assess the relationship of each AE to study drug. To ensure consistency of AE/SAE causality assessments, Investigator(s) should apply the following guideline:

Related: There is an association between the event and the administration of study drug, a plausible mechanism for the event to be related to the study drug and causes other than the study drug have been ruled out, and/or the event re-appeared on re-exposure to the study drug.

Possibly Related: There is an association between the event and the administration of the study drug and there is a plausible mechanism for the event to be related to study drug, but there may also be alternative etiology, such as characteristics of the subject's clinical status or underlying disease.

Unlikely Related: The event is unlikely to be related to the study drug and likely to be related to factors other than study drug.

Not Related: The event is related to an etiology other than the study drug (the alternative etiology must be documented in the study subject’s medical record).

9.2.3. Classifying Action Taken with Study Drug

In the case of an AE, the actions that can be taken with study drug are defined below in [Table 16](#).

Table 16: Options for Action Taken with Study Drug

Classification	Definition
Dose Not Changed	Study drug dose not changed in response to the AE
Dose Reduced	Study drug dose reduced in response to an AE
Drug Interrupted	Study drug administration interrupted in response to an AE
Drug Withdrawn	Study drug administration permanently discontinued in response to an AE
Not Applicable	Action taken regarding study drug administration does not apply. “Not applicable” should be used in circumstances when no opportunity to decide whether to continue, interrupt or withdraw treatment was possible such as when the investigational treatment had been completed before the adverse event began.

9.2.4. Classifying Adverse Event Outcome

For every AE/SAE, the possible outcomes of the event and the definition of the outcome are shown below in [Table 17](#). One outcome must be entered into the appropriate field on the AE and (if appropriate) SAE form for each event as discussed in the eCRF instructions.

Table 17: Classification and Definition of AE Outcomes

Classification	Definition
Recovered / Resolved	Resolution of an AE with no residual signs or symptoms
Recovered / Resolved with sequelae	Resolution of an AE with residual signs or symptoms
Is Recovering / Is Resolving	Incomplete improvement to date but AE continues to improve/resolve and complete resolution is expected over time
Not Recovered / Not Resolved	Either incomplete improvement or no improvement of an AE, such that it remains ongoing
Fatal	Outcome of an AE is death. “Fatal” should be used when death is at least possibly related to the adverse event.
Unknown	Outcome of an AE is not known (e.g., a subject lost to follow up)

9.2.5. Documenting and Reporting Serious Pretreatment Events and Serious Adverse Events

All SAEs that occur after obtaining informed consent through the EOS/Follow-up visit, regardless of causality, must be reported by the Investigator to [REDACTED] and Enanta Pharmaceuticals, Inc., within 24 hours of learning of its occurrence. In addition, all SAEs that occur after the EOS Visit and that are considered related to study drug(s) and all deaths must also be reported within 24 hours of learning of its occurrence. Additional details are provided in the Safety Management Plan. The eCRF should be completed for new/initial events as well as to report follow-up information on previously reported events in the same way as for AEs. Upon stating the seriousness, further details should be provided in the eCRF. Investigators are asked report follow up information as soon as it becomes available, to ensure timely reporting to Health Authorities.

The SAE Form should be sent to the [REDACTED] group via fax or email in case the eCRF is not available:

[REDACTED]
Email (back up): [REDACTED] (US)
Email (back up): [REDACTED] (non-US)
Fax (back up): [REDACTED]
Fax (back up): [REDACTED]

SAEs will be recorded on the SAE Form using a recognized medical term or diagnosis that accurately reflects the event. SAEs will be assessed by the Investigator for severity, relationship to the investigational study drug(s) and possible etiologies. Relationship to study drug(s) will be recorded as related or not related on the SAE form. For the purposes of study analysis, if the event has not resolved at the end of the study reporting period, it will be documented as ongoing. For purposes of regulatory safety monitoring, the Investigator is required to follow the event to resolution and report the outcome of the event to the [REDACTED] using the SAE Form.

The Investigator is responsible for notifying [REDACTED]/the Sponsor within 24 hours of identifying an SAE, regardless of the presumed relationship to the investigational study drug. The SAE Form should be completed for new/initial events as well as to report follow-up information on previously reported events. The Investigator is asked to report follow-up information as it becomes available.

Enanta Pharmaceuticals, Inc. or its designees, as study sponsor, is responsible for reporting suspected, unexpected, serious adverse reactions (SUSARs) involving the study drug(s) to all regulatory authorities, and participating PIs, in accordance with FDA, International Conference on Harmonization (ICH) Guidelines, and/or local regional or country regulatory requirements, as applicable.

9.2.6. Documenting and Reporting of Pregnancy

While females of childbearing potential are allowed in the study, they must agree to use two effective methods of contraception from Screening until 90 days after the last dose of study drug.

However, as a precaution, subjects will be counseled to inform the Investigator of any pregnancy that occurs during study treatment and for 90 days after the last dose of study drug/s.

If a female subject or the female partner of a male subject becomes pregnant while participating in the study, study treatment must be permanently discontinued immediately. The Investigator must notify the Sponsor's Medical Monitor and [REDACTED] within one business day of the sites' knowledge of the subject's (or partner's) pregnancy, by utilizing the study-specified pregnancy report form. If confirmed to be on active drug, the subject or partner will be followed until end of pregnancy and the infant will be followed for one year after the birth, provided informed consent is obtained. A separate ICF will be provided to explain these follow-up activities. Pregnancy itself does not constitute an AE.

9.3. Follow-up of Adverse Events and Serious Adverse Events

Follow all AEs (serious and nonserious) until resolution or otherwise explained (see [Table 17](#)), the subject dies, the event stabilizes and is not expected to further resolve with the maximum time limit for stabilization defined as 30 days after the occurrence of the event, or when alternative therapy is instituted, whichever occurs first. If alternative therapy is instituted, it should be documented. Enanta Pharmaceuticals, Inc., may request that the Investigator perform or arrange for supplemental measurements or evaluations to further clarify the nature of the event.

9.4. Sponsor's Review of Adverse Events and Serious Adverse Events

Enanta Pharmaceuticals, Inc., will maintain an ongoing review of all AEs and SAEs.

9.5. Data Safety Monitoring Board

Safety data from this study will be reviewed by a Data Safety Monitoring Board (DSMB) throughout the study. The DSMB will be headed by a DSMB Chair and will include physicians with expertise in diseases of the liver including NASH. Procedures for data review including timing and potential outcomes will be governed by the DSMB charter.

10. SUBJECT SAFETY MANAGEMENT

In the event that two or more subjects experience a similar drug-related Grade 3 or 4 AE or SAE or Grade 3 or 4 laboratory abnormality, a DSMB meeting will be immediately convened by the Sponsor. Based on the data presented, a decision will be made as to whether or not enrollment should be halted, the study should be halted, or if dosing and enrollment into the study should continue.

10.1. Individual Subject Stopping Rules

Study drug will be discontinued in subjects with elevated ALT or AST (see below) and thorough evaluation and follow-up will be performed:

- If ALT or AST increases to $>5 \times$ Baseline
- If ALT or AST increase $>2 \times$ Baseline AND the increase is accompanied by a concomitant total bilirubin increase to $>2 \times$ Baseline OR the INR concomitantly increases by >0.2
- If elevations of ALT/AST are accompanied by signs or symptoms of right upper quadrant abdominal pain, anorexia, nausea, vomiting, fever, eosinophilia, and/or rash

For subjects who meet the discontinuation criteria and have evidence of liver injury, additional PK samples will be obtained at the same visits as safety labs.

Please refer to Section 10.2 for the close monitoring for subjects who meet criteria for drug discontinuation due to elevated ALT/AST.

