6.1. Blinding of Study Samples

6.1.1. Blinding of NASH Biomarkers, Fibrosis and Inflammatory Markers, MRI/MRE, and Laboratory Liver Test Results

Investigators, site personnel, and CRO/Sponsor will be blinded to the following laboratory tests postbaseline:

- Biomarker laboratory data
 - FGF-19, total BAs
 - C4 [7 α -OH-4-cholesten-3-one]
 - CK18
 - GLP-1
- Fibrosis and inflammatory markers
 - ELF Panel (ie, hyaluronic acid [HA], procollagen III amino terminal peptide [PIIINP], and tissue inhibitor of metalloproteinase 1 [TIMP-1])
 - PRO C3
 - Fibrinogen, CRP, alpha2 macroglobulin and Haptoglobin
 - Tumor necrosis factor alpha and beta (TNF- α and β)
 - Interleukin (IL)-6. IL1 β
 - APRI
 - NFS
 - FIB-4
- Liver Tests
 - ALT

- AST
- GGT

However, abnormal liver test results will be flagged if the lab results are $\geq 2 \times$ baseline and these flagged results will be shared with the Investigator and the Medical Monitor (and/or designee) for safety monitoring purposes.

MRI and MRE results postbaseline will be blinded to the Investigators, site personnel, and Sponsor. Additionally, the MRI facility and radiologist will be blinded to the subject's study treatment and the MRI and MRE readings will be read centrally.

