10.2. Management of Liver Enzyme Elevations

The FDA Guidance for Industry for Drug Induced Liver Injury (*FDA*, 2009) will provide guidance for the management of changes in liver transaminases (ALT/AST) and total bilirubin.

The following close observation guidelines will apply to subjects for whom the repeat assessment shows persistent elevations of transaminases, but who do not meet drug discontinuation criteria, and for subjects who discontinue study drug due to ALT/AST elevations.

The protocol also includes an algorithm to respond to changes in liver enzymes and functions as follow:

- To establish a baseline utilizing at least 2 lab values at least several weeks apart
- For subjects with elevated baseline liver chemistry that develop AST or ALT elevations $2 \times$ baseline, subjects will be reassessed promptly (eg, 48–72 hours) with full liver biochemistry and physical exam and if the repeat assessment shows persistent elevations in transaminases, subjects should be followed according to the “close observation” guidelines:
 - Repeat liver enzyme and serum bilirubin tests two or three times weekly. Frequency of repeat testing can decrease to once a week or less if

- abnormalities stabilize or the trial drug has been discontinued and the subject is asymptomatic.
- Collect additional PK samples at the same visits as safety labs
 - Obtain a more detailed history of symptoms and prior or concurrent diseases.
 - Obtain a history of concomitant drug use (including nonprescription medications and herbal and dietary supplement preparations), alcohol use, recreational drug use, and special diets.
 - Rule out acute viral hepatitis types A, B, C, D, and E; autoimmune or alcoholic hepatitis; NASH; hypoxic/ischemic hepatopathy; and biliary tract disease.
 - Obtain a history of exposure to environmental chemical agents.
 - Obtain additional tests to evaluate liver function, as appropriate (eg, INR, direct bilirubin).
 - Consider gastroenterology or hepatology consultations.
 - Consider liver biopsy for any patient with persistent evidence of liver injury.
- For subjects with alkaline phosphatase (ALP) elevations of $2 \times$ ULN, subjects will be reassessed promptly (eg, 48–72 hours) with full liver biochemistry and physical exam. Labs should be repeated until resolution. Above guidelines for close monitoring should also apply.
 - If a subject lives in a remote area, they can be tested locally with the results promptly communicated to the Investigator site

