9. Height to be assessed at Screening only
10. Full physical exam (PE) at screening and EOS Visit; subsequent PE should be targeted to review new signs and symptoms
11. Vital Signs include heart rate, respiratory rate, blood pressure, and will be measured once in the morning before the morning dose of study drug
12. Safety laboratory tests include chemistry (including liver function tests), hematology, and urinalysis and should be collected predose at all visits; See [Table 15](#) for details. Creatinine clearance will be calculated based on serum creatinine value performed all visits.. HbA1c will be obtained at Screening, Baseline, and Week 12 only
13. Lipids and CV risk markers to be collected are detailed in [Table 15](#)
14. Markers of inflammation include fibrinogen, CRP, IL6, IL1 β , TNF- α , TNF- β , alpha2 macroglobulin and haptoglobin (See [Table 15](#))
15. Samples will be collected from all subjects predose. Additional samples may be collected to further assess safety events.
16. Samples should be collected after a minimum 8 hr fast and before the subject takes the daily dose of study drug. All samples collected Day 1, Weeks 2, 4, 8 and 12 at predose and two samples postdose; with the first sample collected 1 to 3 hours postdose and the second sample collected at least 1 hour later
17. Collect PK/PD samples after a minimum 8 hr fast and before the daily dose of study drug. PK/PD samples on Days 1 and 84 (Week12) collected predose and 2, 6, and 8 hr postdose; Weeks 2, 4 and 8 at predose and two samples postdose with the first sample collected 1 to 3 hours postdose and the second sample collected at least 1 hr later
18. PK predose samples should be collected after a minimum 8 hour fast before the daily dose of study drug. PK samples collected Day 1, Weeks 2, 4, 8 and 12 at predose and two samples postdose; the first sample collected 1 to 3 hours postdose and the second sample at least 1 hour later. For subjects with persistent transaminase or ALP elevations, and have evidence of liver injury and who remain on study drug, [REDACTED].
19. Study drug given in the clinic on days where subject is seen in the clinic

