8.7.2 Stopping Rules

Summaries will be provided using counts and percentages for subjects who meets the stopping rules as described below:

- ALT or AST > 5 x Baseline
- ALT or AST > 2 x Baseline AND concomitant total bilirubin > 2 x Baseline OR Concomitant INR > 0.2 from Baseline
- ALT or AST > Baseline AND Right Upper Quadrant Abdominal Pain, Anorexia, Nausea, Vomiting, Fever, Eosinophilia, and/or Rash

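### Stopping rule 3 has no ALT/AST multiple and the SAP counts any rise above baseline, while sites are shown only results at 2x or more; rule 2's INR limb rests on a discretionary test

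*Protocol*

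**What the plan says.** **Rule 3.** Protocol 10.1 gives three hepatic stopping rules. Rule 1 is ALT or AST above 5x baseline. Rule 2 is ALT or AST above 2x baseline with bilirubin above 2x baseline, or with an INR rise of more than 0.2. Rule 3 reads "If elevations of ALT/AST are accompanied by signs or symptoms of right upper quadrant abdominal pain, anorexia, nausea, vomiting, fever, eosinophilia, and/or rash", with no multiple and no reference value. SAP 8.7.2 tabulates it as "ALT or AST > Baseline AND Right Upper Quadrant Abdominal Pain, Anorexia, Nausea, Vomiting, Fever, Eosinophilia, and/or Rash".

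**What the site sees.** For ALT, AST and GGT among other tests, Protocol 6.1.1 states that "Investigators, site personnel, and CRO/Sponsor will be blinded to the following laboratory tests postbaseline". The exception is a liver test at 2x baseline or more: "these flagged results will be shared with the Investigator and the Medical Monitor (and/or designee) for safety monitoring purposes".

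**Rule 2 and INR.** SAP 8.7.2 tabulates rule 2 as a single composite: "ALT or AST > 2 x Baseline AND concomitant total bilirubin > 2 x Baseline OR Concomitant INR > 0.2 from Baseline". In Protocol Table 19, INR is marked at Screening and at the End of Study visit only. Footnote 12 defines the all-visit panel: "Safety laboratory tests include chemistry (including liver function tests), hematology, and urinalysis and should be collected predose at all visits". Table 15 lists INR under coagulation, apart from chemistry. After a 2x rise, Protocol 10.2 calls for prompt reassessment, for example at 48 to 72 hours, "with full liver biochemistry and physical exam and if the repeat assessment shows persistent elevations in transaminases", close observation begins. INR is first named there: "Obtain additional tests to evaluate liver function, as appropriate (eg, INR, direct bilirubin".

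**The concern.** A stopping-rule table should tell the reader how many subjects met the rule that sites were asked to apply. Here the protocol leaves the rule 3 threshold open, the SAP sets it at any value above baseline, and the release rule hides everything below 2x. The reported count could then include subjects whose investigator had no reason to stop drug. The SAP also joins the rise and the symptom with a bare AND, although its own rule 2 requires concomitance and the protocol's rule 3 has the symptom accompany the rise. A slightly raised ALT at one visit and a rash at another would satisfy the SAP wording.

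Because EDP-305 is expected to lower ALT, a condition of being above baseline is met less often on active drug for that reason alone. A hepatic safety table built on it could make the drug look protective.

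The INR point concerns conduct. Rule 2 obliges the site to stop drug in a subject with ALT/AST above 2x, bilirubin not above 2x and INR up by more than 0.2. That subject is found only if someone chooses to order the test.

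**Working it through.** No figure stated in the plan bears on this point, so there is none to reproduce. The check is a comparison of text, a count from the schedule, and one illustration.

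**1. Thresholds side by side**

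| Place | ALT/AST level |
|---|---|
| Protocol 10.1 rule 1 | above 5x baseline |
| Protocol 10.1 rule 2 | above 2x baseline |
| Protocol 10.1 rule 3 | none given |
| Protocol 6.1.1 release to site | 2x baseline or more |
| Protocol 10.2 reassessment | 2x baseline |
| SAP 8.7.2 rule 3 | above baseline |

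The SAP's rule 3 level is not a stated ALT/AST action level anywhere in the protocol. Between 1x and 2x, a subject who is never flagged or retested is counted by the SAP but not shown to the site.

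**2. INR opportunities**

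The on-treatment visits after the first dose are Day 3 and Weeks 2, 4, 8 and 12, five in all. Safety chemistry is marked at 5 of 5 and INR at 0 of 5. The End of Study INR comes four weeks after the last dose, so it cannot trigger a dosing stop. Total bilirubin is part of the all-visit chemistry and is not on the blinded list, so rule 2's bilirubin limb works as written.

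**3. How often ALT exceeds baseline (illustration only)**

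Inputs from Protocol 11.2: mean ALT change -10 on placebo and -40 on EDP-305, SD 40. Planned arm sizes from Protocol 5.6: 25 placebo, 50 per dose. Assumption: change is normally distributed.

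P(ALT above baseline) = P(change > 0) = 1 - Phi((0 - mean)/SD)

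- Placebo: 1 - Phi(10/40) = 1 - Phi(0.25) = 0.4013; 0.4013 x 25 = 10.0 subjects.
- Each EDP-305 arm: 1 - Phi(40/40) = 1 - Phi(1.00) = 0.1587; 0.1587 x 50 = 7.9 subjects.
- Ratio: 0.4013 / 0.1587 = 2.5.

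The documents give no symptom rate. Suppose a listed symptom is present in 10% to 40% of each arm, independently of ALT (both are assumptions). The share meeting the SAP's rule 3 on ALT at that one visit is then:

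- Placebo: 0.10 x 0.4013 = 4.0% to 0.40 x 0.4013 = 16.1%.
- EDP-305: 0.10 x 0.1587 = 1.6% to 0.40 x 0.1587 = 6.3%.

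This difference arises with no difference in liver injury between arms. It is a single-visit, Week 12 calculation for ALT only. It should not be extended to earlier visits, because Protocol 4.2.1 expects enzyme reductions only after more than one month of therapy.

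**The case against.** **The SAP may be transcribing the rule literally.** Rules 1 and 2 carry multiples and rule 3 does not, so a symptom-triggered rule covering any rise is a fair reading, and the SAP's wording fits it. This stands. A reader might infer that 2x was intended and that the SAP is simply wrong. The documents do not settle that, and the threshold is a clinical choice. The point needs only the mismatch: if any rise was meant, the release rule works against it; if 2x was meant, the SAP over-counts.

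**Sites have other routes to a value.** It is tempting to say that rule 3 cannot be applied at all between 1x and 2x. That goes too far. Protocol 8.4 lets investigators order additional laboratory tests. Protocol 10.2 provides for repeat enzymes under close observation and local testing for subjects in remote areas. The gap is therefore confined to subjects never flagged or retested. The 10.2 routes open mainly after a 2x rise, so they do not close it.

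**The INR limb can be reached.** Any ALT/AST above 2x is flagged, and an INR can then be ordered. Protocol 10.2 also refers to regulatory guidance on drug-induced liver injury. Calling the limb inoperable would be wrong; it is discretionary where the stop is mandatory.

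**The model is crude.** At a baseline of 50 IU/L it puts Phi((-50 + 40)/40) = Phi(-0.25) = 40% of EDP-305 subjects below zero ALT at Week 12, and Phi((-50 + 10)/40) = Phi(-1) = 16% of placebo subjects. In true liver injury, symptoms would also not be independent of ALT. Hence the figures are illustrative only; the textual finding does not need them.

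**The consequence is limited.** SAP 8.7 plans no safety tests, and this is one descriptive table. The table shells, DSMB charter, Laboratory Manual and Safety Management Plan were not available and may settle some of the detail.

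**Conclusion.** The point holds, as a minor one. Protocol 10.1 leaves rule 3 without a threshold. SAP 8.7.2 counts any rise above baseline with an unlinked symptom. Protocol 6.1.1 shows sites only results at 2x or more. For subjects never flagged or retested, the table would count events that the site could not act on. If Week 12 ALT behaves roughly as planned, the ALT condition alone would be met by about 40% of placebo and 16% of each EDP-305 arm. The table would then mostly describe noise and the efficacy effect. Those percentages rest on normality and on the sample-size assumptions.

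For rule 2, INR-only cases can be missed, because INR is scheduled at none of the five relevant visits and is otherwise left to judgement after a persistent repeat.

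A reader might infer that subjects are left unprotected. The documents do not support that: rule 1, the bilirubin limb of rule 2, DSMB review (Protocol 9.5) and close observation (Protocol 10.2, SAP 8.7.2.1) all remain. The DSMB does not fill the rule 3 gap, however, because neither document gives it a trigger for an individual subject under that rule.

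**What to change.** (a) State one rule 3 threshold in both Protocol 10.1 and SAP 8.7.2, matched to what sites receive. The default would be 2x baseline or more. If the clinical team wants a lower threshold, release ALT/AST when a listed symptom is reported. In SAP 8.7.2, require the symptom to be concurrent with the rise.

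(b) Require a reflex INR, compared with the Screening INR, at the first 48 to 72 hour reassessment after any ALT/AST flag at 2x or more.

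**Cost.** A clarifying amendment, revised SAP wording, and one added tube at a reassessment that Protocol 10.2 already requires, so no extra visit. At 2x there would be no rule 3 action between 1x and 2x, which the clinical team should accept explicitly. The lower-threshold option would show sites more post-baseline results for the primary efficacy variable.
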